#### **4.3 Justification for dose**

Healthy study participants enrolled in UP0141 will receive a single weight-tiered dose of rozanolixizumab, as summarized in Table 4-1, administered using a commercially available syringe driver. The proposed weight-tiered doses of rozanolixizumab are consistent with the recommended doses in the FDA-approved US Prescribing Information (RYSTIGGO, 2023).

**Table 4-1: Rozanolixizumab weight tiers**

Body weight of study participant	Dose	Volume to be infused
<50kg	420mg	3mL
≥50kg to <100kg	560mg	4mL
≥100kg	840mg	6mL

#### 4.4 End of study definition

A study participant is considered to have completed the study if she has completed all periods of the study including the SFU or the last scheduled procedure shown in the schedule of activities (Section 1.3).

End of study is defined as the date of the last scheduled procedure shown in the schedule of activities for the last study participant in the study.

### 5 STUDY POPULATION

The study will enroll adult (≥18 years of age) healthy lactating women who on Day 1 of the study (rozanolixizumab dosing day) will be at least 6 weeks postpartum and who have voluntarily decided, prior to having knowledge of the study, to wean their infant(s). Additionally, to be eligible to participate in the study, participants must agree to collect all expressed breast milk over the 7-day Sampling Period and to not resume breast milk feeding (by any means) or donate expressed breast milk between the end of the breast milk Sampling Period and the SFU telephone call 8 weeks after dosing (ie, on Day 57). Participants may decide to resume breast milk feeding 8 weeks after administration of rozanolixizumab, with the agreement that any breast milk collected (to maintain milk supply) during that 8-week period will be discarded (Section 4.2).

Prospective approval of protocol deviations to recruitment and enrollment criteria, also known as protocol waivers or exemptions, is not permitted.

#### 5.1 Inclusion criteria

Participants are eligible to be included in the study only if all the following criteria apply:

##### Age

1. Study participant must be minimum 18 years at the time of signing the ICF.

##### Type of participant and disease characteristics

2. Study participant is overtly healthy as determined by medical evaluation including medical history, physical examination, laboratory tests, and cardiac monitoring.
3. Study participant has a body temperature between 35.0°C and 37.5°C, inclusive on Day 1.
4. Study participant is lactating and will be at least 6 weeks postpartum on Day 1 of the study.

5. Study participant has voluntarily decided, prior to having knowledge of this study, to cease breast milk feeding (by any means) in relation to her current period of lactation.

Study participant agrees to cease or suspend breast milk feeding by Day 1 of the study and to not resume breast milk feeding (by any means) or donate expressed breast milk for 8 weeks following administration of rozanolixizumab. Participants may decide to resume breast milk feeding 8 weeks after administration of rozanolixizumab, with the agreement that any breast milk collected (to maintain milk supply) during that 8-week period will be discarded.

6. Study participant agrees to maintain an adequate milk supply through regular breastfeeding or pumping (eg, pumping 3 to 4 times per day) for at least 4 weeks prior to Day 1 of the study and to collect all expressed breast milk over the 7-day Sampling Period.
7. Alternative nutritional sources to breast milk have already been established for the study participant's infant(s).
8. As assessed by the investigator, study participant has sufficient breast milk production to meet the breast milk requirements of the study.

### Weight

9. Study participant has body weight  $\geq 35\text{kg}$  at Screening and body mass index  $\geq 18.5\text{kg/m}^2$ .

### Sex

10. Study participant is female.

- A female participant is eligible to participate if she is not pregnant (see Appendix 4 [Section 10.4]) and at least 1 of the following conditions applies:
  - A woman of childbearing potential (WOCBP) who agrees to follow the contraceptive guidance in Appendix 4 (Section 10.4) during the Sampling Period and for at least 1 week after the last dose of study treatment.

OR

- Not a WOCBP (ie, premenopausal female with documented hysterectomy, documented bilateral salpingectomy, or documented bilateral oophorectomy).

### Informed Consent

11. Study participant is capable of giving signed informed consent as described in Appendix 1 (Section 10.1.3) which includes compliance with the requirements and restrictions listed in the ICF and in this protocol.

## 5.2 Exclusion criteria

Participants are excluded from the study if any of the following criteria apply:

### Medical conditions

1. Study participant has history or presence of/significant history of or current cardiovascular, respiratory, hepatic, renal, gastrointestinal, endocrinological, hematological, neurological disorders, or chronic infectious diseases capable of significantly altering the absorption,

metabolism, or elimination of drugs; constituting a risk when taking the study intervention; or interfering with the interpretation of data.

2. Study participant has any medical, obstetrical, or psychiatric condition, or plans a surgical intervention that, in the opinion of the investigator, could jeopardize or would compromise the study participant's ability to participate in this study.
3. Study participant has history of breast implants, breast augmentation, or breast reduction surgery.
4. Study participant has clinically significant multiple or severe drug allergies.
5. Study participant has a known hypersensitivity to any components of the study medication or other anti-FcRn medications, or has a known history of hyperprolinemia, since L-proline is a constituent of the rozanolixizumab formulation.
6. Study participant has alanine aminotransferase (ALT), aspartate aminotransferase (AST), or alkaline phosphatase (ALP)  $>1.0 \times$  upper limit of normal (ULN). Tests that result in ALT, AST, or ALP up to 25% above the exclusion limit may be repeated once for confirmation. This includes rescreening. If the repeat values are below the ULN, the study participant will be considered to not meet the exclusion criteria.
7. Study participant has bilirubin  $>1.0 \times$  ULN (isolated bilirubin  $<1.5 \times$  ULN is acceptable if bilirubin is fractionated and direct bilirubin  $<35\%$ ). For study participants with a Baseline result  $>ULN$  for total bilirubin, a Baseline diagnosis and/or the cause of any clinically meaningful elevation must be understood and recorded in the case report form (CRF).
8. Study participant has current or chronic history of liver disease, or known hepatic or biliary abnormalities (with the exception of Gilbert's syndrome or asymptomatic gallstones).
9. Study participant has 12-lead electrocardiogram (ECG) with abnormalities considered to be clinically significant upon medical review.
10. Study participant has had lymphoma, leukemia, or any malignancy within the past 5 years except for basal cell or squamous epithelial carcinomas of the skin that have been resected with no evidence of metastatic disease for 3 years.
11. Study participant has absolute neutrophil count  $<1.5 \times 10^9/L$  and/or lymphocyte count  $<1.0 \times 10^9/L$ .
12. Study participant has history of known inflammatory bowel disease, active diverticular disease, or a history of confirmed duodenal, gastric, or esophageal ulceration in the previous 6 months.

### **Prior/Concomitant therapy**

13. Study participant has past or intended use of over-the-counter or prescription medication (including herbal medications) within 14 days prior to dosing until the end of the Sampling Period (specific medications listed in Section 6.5.1 are allowed).
14. Study participant has received live vaccine(s) within 4 weeks prior to Screening or plans to receive such vaccines during the study.
15. Study participant has received treatment with biologic agents (such as monoclonal antibodies including marketed drugs) within 3 months or 5 half-lives (whichever is longer) prior to dosing.

### **Prior/Concurrent clinical study experience**

16. Study participant donated or lost >500mL of blood or blood products in the 4 weeks preceding the start of dosing or plans to donate blood during the study.
17. Study participant has had exposure to more than 3 new chemical entities within 12 months prior to dosing.
18. Study participant has previously participated in this study or participant has previously been assigned to treatment in a study of the medication under investigation in this study.
19. Study participant has participated in another study of an investigational medicinal product (IMP) (and/or an investigational device) within the previous 90 days or 5 half-lives prior to Day -1 (whichever is longer) or is currently participating in another study of an IMP (and/or an investigational device).

### **Diagnostic assessments**

20. Study participant has IgG <5.5g/L at Screening.
21. Study participant has positive prestudy drug/alcohol screen.

### **Other exclusions**

22. Study participant has had an active clinically significant infection within the last 6 weeks.  
Note: Study participants with mastitis at Screening that do not meet the criteria for clinically significant infection may be rescreened after the infection is completely resolved.
23. Study participant smoked on average >5 cigarettes/day (or equivalent) during the last 3 months and is not able to stop smoking during the Sampling Period.
24. Study participant has history of alcohol and/or drug abuse up to 12 months before Screening. Alcohol abuse is defined as follows: study participant has an alcohol consumption of more than 14 units per week (1 unit of alcohol is equivalent to 10mL ethanol; for example, 330mL of 5% alcohol by volume beer=1.7 units; 125mL of 12% wine=1.5 units; 50mL of spirits=2 units).
25. Study participant has regular use of known drugs of abuse.

## **5.3 Lifestyle restrictions**

No lifestyle restrictions are required.

## **5.4 Screen failures**

Screen failures are defined as study participants who consent to participate in the clinical study but are not subsequently entered in the study. A minimal set of screen failure information is required to ensure transparent reporting of screen failure study participants to meet the Consolidated Standards of Reporting Trials publishing requirements and to respond to queries from regulatory authorities. Minimal information includes demography, screen failure details, eligibility criteria, and any serious adverse event (SAE).

Individuals who do not meet the criteria for participation in this study (screen failure) may be rescreened under certain circumstances (eg, resolution of mastitis infection). Rescreening must be discussed with the Medical Monitor, with a decision to rescreen made on a case-by-case basis.

Tests that result in ALT, AST, or ALP up to 25% above the exclusion limit may be repeated once for confirmation. This includes rescreening.

## **6 STUDY TREATMENTS**

Study treatment is defined as any investigational treatment(s), marketed product(s), placebo, or medical device(s) intended to be administered to a study participant according to the study protocol.

### **6.1 Treatments administered**

Study treatment details are presented in [Table 6-1](#).

**Table 6-1: Study treatments**

Arm name	Rozanolixizumab
Intervention name	Rozanolixizumab
Type	Biologic
Dose formulation	Solution for injection
Unit dose strength	A 6mL glass vial, containing no less than 2.0mL extractable volume of rozanolixizumab at a concentration of 140mg/mL
Dosage levels	Single dose of 420mg for study participants <50kg, 560mg for participants ≥50kg to <100kg, or 840mg for participants ≥100kg
Route of administration	Subcutaneous infusion
Use	Experimental
IMP and NIMP/AxMP	IMP
Sourcing	Provided centrally by the sponsor
Packaging and labeling	Packaging will be described in the IMP Handling Manual. Packaging will be labeled as required per country requirement.
Excipients	Rozanolixizumab at a concentration of 140mg/mL, formulated with 30mM L-histidine, 250mM L-proline, 0.03% (w/v) polysorbate 80, at pH 5.6
Former name	UCB7665

AxMP=auxiliary medicinal product; IMP=investigational medicinal product; NIMP=noninvestigational medicinal product

### 6.1.1 Medical devices

The approved medical devices (not manufactured by or for UCB) provided for use in this study are:

- Drug delivery devices
- Breast milk pump

All medical device deficiency (including malfunction use error, and inadequate labeling) shall be documented and reported by the investigator throughout the study (see Section 8.3.8) and appropriately managed by the sponsor.

### 6.2 Preparation, handling, storage, and accountability requirements

The investigator or designee must confirm that appropriate temperature conditions have been maintained during transit for all study treatment received, and any discrepancies are reported and resolved before use of the study treatment.

Only study participants enrolled in the study may receive study treatment and only authorized site staff may supply or administer study treatment. All study treatments must be stored in a secure, environmentally controlled, and monitored (manual or automated) area in accordance with the labeled storage conditions, with access limited to the investigator and authorized site staff.

The investigator, institution, or the head of the medical institution (where applicable) is responsible for study treatment accountability, reconciliation, and record maintenance (ie, receipt, reconciliation, and final disposition records).

In case an out-of-range temperature is noted, it must be immediately reported as per instructions contained in the IMP Handling Manual.

Further guidance and information for the final disposition of unused study treatment are provided in the IMP Handling Manual.

### **6.2.1 Drug accountability**

The CRF will be used to record study medication dispensing and return information on a by-study participant basis and will serve as source documentation during the course of the study. Details of any study medication lost, damaged (due to breakage or wastage), not used, partially used, disposed of at the study site, or returned to the sponsor or designee must also be recorded on the appropriate forms. All supplies and pharmacy documentation must be made available throughout the study for UCB (or designee) to review.

The investigator (or designee) is responsible for retaining all used, unused, and partially used containers of study medication until returned or destroyed.

The investigator may assign some of the investigator's duties for drug accountability at the study site to an appropriate pharmacist/designee.

The investigator must ensure that the study medication is used only in accordance with the protocol.

Periodically, and/or after completion of the clinical phase of the study, all used (including empty containers/partially used), unused, damaged, and/or expired study medication must be reconciled and either destroyed at the site according to local laws, regulations, and UCB standard operating procedures or returned to UCB (or designee). Investigational medicinal product intended for the study cannot be used for any other purpose than that described in this protocol.

## **6.3 Measures to minimize bias: randomization and blinding**

All study participants will receive a single dose of rozanolixizumab under close and continued attention of the investigator or designee; thus, there is no opportunity for bias. Based on this study design, (ie, open-label), randomization and blinding are not possible and are therefore not applicable to this study.

## **6.4 Treatment compliance**

Study participant compliance will be ensured by the administration of study medication by designated site personnel.

## **6.5 Concomitant medication(s)/treatment(s)**

### **6.5.1 Permitted concomitant treatments (medications and therapies)**

Any treatment, including over-the-counter products and supplements, must be recorded in the study participant's notes (source documentation), and provided on the CRF. This record should include the name of the drug, the dose, the route, and date(s) of administration, and the indication for use.

Information on past/prior/concomitant medications will be captured from the first day after delivery, but not exceeding 30 days prior to Screening.

For the purposes of this study:

- Past medications are those that stopped prior to entering the Screening Period (but not exceeding 30 days).
- Prior medications are those that were ongoing or started prior to entering the Screening Period (but not exceeding 30 days).
- Concomitant medications are medications with at least 1 day in common with the Screening or Sampling Period.

Prior medications may include both past medications and concomitant medications.

Permitted concomitant treatments are presented in [Table 6-2](#).

**Table 6-2: Permitted concomitant treatments**

Permitted medications	Dose threshold	Comment
Paracetamol	Every 6 to 8 hours, not exceeding 2g/day, and with a total of no more than 10g per 14 days	With approval from the investigator, paracetamol is permitted for the treatment of mild symptoms (eg, headache or pain)
Ibuprofen	Every 6 to 8 hours, not exceeding 2400mg/day	With approval from the investigator, ibuprofen is permitted for the treatment of mild symptoms (eg, headache or pain)
Hormonal contraceptives, implants, patches, intrauterine hormone-releasing system, or intrauterine devices delivering progesterone	NA	None

NA=not applicable

## 6.5.2 Prohibited concomitant treatments (medications and therapies)

Prohibited concomitant treatments are presented in [Table 6-3](#).

**Table 6-3: Prohibited concomitant treatments**

Prohibited medications	Dose threshold	Comment
Prescription medication (including herbal medications) or over-the-counter medicines	All doses are prohibited from 14 days prior to dosing until the end of the Sampling Period	With the exception of vitamins and the permitted concomitant treatments noted in Section 6.5.1, and unless required to treat an adverse event, including pretreatment
Vaccines	All doses	Vaccinations are not allowed during the study

## 6.6 Dose modification

No dose modifications are allowed during the study.

## 6.7 Criteria for study hold or dosing stoppage

Not applicable.

## 6.8 Treatment after the end of the study

Not applicable. This is a Phase 1 study in healthy participants; therefore, no treatment will be provided after the end of the study.

# 7 DISCONTINUATION OF STUDY MEDICATION AND PARTICIPANT DISCONTINUATION/WITHDRAWAL

## 7.1 Discontinuation of study medication

During the study, study participants will receive a single dose of rozanolixizumab administered subcutaneously. This will be performed under close and continued attention of the investigator or designee.

### 7.1.1 Hypersensitivity stopping criteria

In case of any signs of an infusion reaction or anaphylaxis, the infusion will be stopped immediately, and appropriate treatment will be initiated, as necessary, at the discretion of the investigator. This includes the use of antihistamines for urticaria and appropriate management in case of potentially life-threatening events such as anaphylaxis. Infusion may be restarted in mild reactions only if clinically appropriate. The study participant should be followed until resolution of the event. See Appendix 7 and Appendix 8 (Section 10.7 and Section 10.8, respectively) for procedures to follow in the instance of infusion reactions or anaphylaxis. Study participants will be monitored during treatment with rozanolixizumab and for 15 minutes after the administration is complete for clinical signs and symptoms of hypersensitivity reactions.

### **7.1.2 Liver chemistry stopping criteria**

In UP0141, a single dose of rozanolixizumab will be administered to healthy study participants; therefore, no individual liver chemistry stopping criteria apply.

Specific assessments and follow-up actions for potential drug-induced liver injury are provided in Appendix 5 (Section 10.5).

### **7.1.3 QTc stopping criteria**

No QTc stopping criteria apply.

## **7.2 Study participant discontinuation/withdrawal from the study**

Study participants are free to withdraw from the study at any time without prejudice to their continued care.

A study participant may withdraw from the study at any time at her own request or may be withdrawn at any time at the discretion of the investigator for safety, behavioral, compliance, or administrative reasons.

If the study participant withdraws consent for disclosure of future information, the sponsor may retain and continue to use any data collected before such a withdrawal of consent.

If a study participant withdraws from the study, she may request destruction of any samples taken and not tested, and the investigator must document this in the site study records.

See the schedule of activities (Section 1.3) for data to be collected at the time of study discontinuation and follow up and for any further evaluations that need to be completed.

Study participants who withdraw from the study during the Sampling Period will be asked to undergo the EW Visit procedures and will be encouraged to have a SFU telephone call on Day 57 ( $\pm 5$  days).

Study participants withdrawn from the study will not be allowed to re-enter the study.

A study participant withdrawing from the study before Day 7 may be replaced.

Investigators should contact the Medical Monitor, whenever possible, to discuss the withdrawal of a study participant in advance.

Study participants should be withdrawn from the study if any of the following events occur:

1. Study participant develops an illness that would interfere with her continued participation.
2. Study participant is noncompliant with the study procedures or medications in the opinion of the investigator.
3. Study participant takes prohibited concomitant medications as defined in this protocol (Section 6.5.2).
4. Study participant withdraws her consent.
5. The sponsor or a regulatory agency requests withdrawal of the study participant.
6. Study participant needs a surgical intervention during the Sampling Period.

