### 3 OBJECTIVES AND ENDPOINTS

**Table 3-1: Objectives and endpoints**

Objectives	Endpoints
Primary	

 
To assess the concentration of rozanolixizumab in mature breast milk of healthy study participants following administration of a single dose of rozanolixizumab
 
	
The primary PK endpoint is concentration of rozanolixizumab in breast milk over a 7-day Sampling Period.
 
The secondary PK endpoints are:
 
 
Estimated daily infant dosage
 
Relative infant dose of rozanolixizumab from breast milk
 

Secondary	

 
To assess the safety of a single dose of rozanolixizumab administered to healthy study participants
 
	The secondary safety endpoint is occurrence of TEAEs from Day 1 through the SFU Visit.
Exploratory/Other	

 
To determine PK parameters of rozanolixizumab in mature breast milk and plasma of healthy study participants following administration of a single dose of rozanolixizumab
 
	
The exploratory/other PK endpoints are:
 
 
<math>C_{\max}</math>, <math>t_{\max}</math>, <math>AUC_{(0-7d)}</math> in breast milk and plasma
 
<math>Ae_{7d}</math> and Fe in breast milk
 
Milk:plasma <math>AUC_{(0-7d)}</math> ratio
 

$Ae_{7d}$ =cumulative total amount of drug excreted in milk to Day 7;  $AUC_{(0-7d)}$ =area under the concentration-time curve from 0 to 7 days; d=day;  $C_{\max}$ =maximum plasma concentration; Fe=fraction of dose excreted in milk; PK=pharmacokinetic(s); SFU=Safety Follow-Up; TEAE=treatment-emergent adverse event;  $t_{\max}$ =time to maximum plasma concentration

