### **10.9.2 Suspected aseptic meningitis**

Drug-induced aseptic meningitis is a diagnosis of exclusion after ruling out infectious causes (Jolles et al, 2000). A few cases of DIAM have been reported in the rozanolixizumab program. Consequently, suspected aseptic meningitis is being managed as an AESM (see Section 8.3.7).

Participants should be monitored for signs and symptoms suggestive of CNS involvement and evaluated immediately if meningitis is suspected. A full neurological workup should be performed, including, but not limited to, imaging, eg, computed tomography scan, or preferably gadolinium-enhanced magnetic resonance imaging, a lumbar puncture with cerebral spinal fluid (CSF) analysis inclusive of glucose, protein, differential complete blood count, cultures, gram stain, and/or viral polymerase chain reaction as appropriate. A concurrent blood sample should be collected as per local practice. The ultimate investigative procedures are at the discretion of the investigator or the treating physician. For studies where a neurologist is not the investigator, a neurological consultation is also recommended to aid in decision making and study participant management. These investigations will be performed to further understand the potential mechanisms of DIAM in the participants.

All procedures related to the diagnosis, treatment, and investigation of meningitis should be recorded, and preliminary data should be included on the SAE form used for reporting the event as an AESM within 24 hours (ie, preliminary data reported on the first reporting may not have CSF results yet, but the reporting should occur as soon as there is a suspected diagnosis). Full results should be communicated in subsequent exchanges with the sponsor.

Participants experiencing an event of DIAM should be strongly encouraged to remain in the study. This will allow for monitoring and follow up of the participant, including a complete neurological exam on subsequent physical examinations. Longer-term follow up on any AEs related to DIAM that are ongoing may be warranted until resolution.

Associated symptoms with aseptic meningitis should be managed at the investigator's discretion.

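### Withdrawing participants from the study after the only dose stops data collection rather than treatment, and makes the Day 57 safety call optional for them

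*Protocol*

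**What the plan says.** Treatment is a single administration. Protocol 7.1: "During the study, study participants will receive a single dose of rozanolixizumab administered subcutaneously".

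Protocol 7.2 then lists reasons for leaving the study under the lead-in "Study participants should be withdrawn from the study if any of the following events occur". Among them are "Study participant develops an illness that would interfere with her continued participation", noncompliance in the investigator's opinion, "Study participant takes prohibited concomitant medications as defined in this protocol", and the need for surgery in the Sampling Period. Nothing limits the list to the period before dosing. Those who withdraw in the Sampling Period are asked to complete the Early Withdrawal (EW) Visit and are encouraged to take the Day 57 call. Section 4.1.3 extends the same encouragement to any premature withdrawal. A participant withdrawn before Day 7 may be replaced, and nobody withdrawn may re-enter.

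On vaccines, Protocol Table 6-3 states "Vaccinations are not allowed during the study" and applies this to all doses. Exclusion criterion 14 is narrower: "Study participant has received live vaccine(s) within 4 weeks prior to Screening or plans to receive such vaccines during the study".

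On the safety objective, Protocol Table 3-1 states "The secondary safety endpoint is occurrence of TEAEs from Day 1 through the SFU Visit". SAP 4.3.1.1 sets the window at 56 days after dosing. For drug-induced aseptic meningitis (DIAM), Protocol 10.9.2 states "Participants experiencing an event of DIAM should be strongly encouraged to remain in the study".

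**The concern.** Once the Day 1 dose has been given there is no treatment left to stop, so the 7.2 list can only end observation. The sponsor recognised this elsewhere: Protocol 7.1.2 drops individual liver stopping criteria because only one dose is given. Section 7.2 does not follow the same logic.

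Two sets of data are exposed. The first is the TEAE endpoint, which closes with the Day 57 call. That call becomes optional for a withdrawn participant, although she stays in the Safety Set. The second is the milk profile to 144 h, on which AUC(0-7d), the milk:plasma ratio, the estimated daily infant dosage and the relative infant dose all depend.

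The surrounding passages also do not fit together. A planned non-live vaccine is not an exclusion but is a withdrawal trigger once given. Aseptic meningitis could qualify as an interfering illness under 7.2, while 10.9.2 asks for retention.

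**Working it through.** The plan has no figure to reproduce here. The 12 to 15 participants are a feasibility number (Protocol 9.8, SAP 5), and no withdrawal rate is given.

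**Does the list apply after dosing?** Yes. The surgery reason operates in the Sampling Period, which SAP 4.1.1.1 defines as Days 1 to 7.

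**TEAE window.** Days not covered by scheduled contact if the call is missed = 56 − days since dosing at withdrawal.
- Withdrawal at 24 h: 56 − 1 = 55 of 56 days (98%).
- Withdrawal at 144 h: 56 − 6 = 50 of 56 days (89%).
- Withdrawal on Day 21, for example after a vaccine: 56 − 20 = 36 of 56 days (64%).

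The schedule of activities has no visit between Day 7 and the Day 57 call. The EW Visit is requested only for withdrawal in the Sampling Period, so the Day 21 case has no required contact at all.

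**Milk intervals.** Protocol Table 1-1 gives four 3-hour intervals to 12 h and eleven 12-hour intervals from 12 to 144 h, so 15 after dosing. Those starting at or after withdrawal are uncollected, apart from any EW sample.
- 24 h: 10 of 15
- 48 h: 8 of 15
- 72 h: 6 of 15
- 96 h: 4 of 15
- 144 h or later: 0 of 15

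Missing PK data are not imputed (SAP 6.9), and AUC(0-7d) is defined to 144 h (SAP Table 6-2).

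**Weight of one participant.** 1/15 = 6.7% to 1/12 = 8.3% of the Safety Set, taking its size as the planned 12 to 15.

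**How likely is at least one withdrawal?** With assumed rate w, the chance is 1 − (1 − w)^n.
- n = 12: 46%, 72% and 93% for w = 5%, 10% and 20%.
- n = 15: 54%, 79% and 96% for the same rates.

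**Effect on the PK summaries.** SAP 6.10.2 gives full statistics if at least two thirds of participants have the parameter: 8 of 12 or 10 of 15, so 4 or 5 may be missing. For n = 12 the chance of exceeding that is 0.02%, 0.4% and 7% at the three assumed rates. Losing a whole parameter summary this way is unlikely; losing individual profiles is not.

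**Effect on what zero events can show.** As an illustration only, since the SAP plans no such bound, the exact one-sided 95% upper limit with no events is 1 − 0.05^(1/n). It is 22.1% for n = 12 and 18.1% for n = 15. With only 10 followed to Day 57 it is 25.9%.

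**The case against.** The strongest reply is that the plan already limits the damage, and much of it stands.

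- The EW Visit includes blood, milk and AE review, and the Day 57 call is offered to every withdrawn participant. If the call takes place, the window is covered. Protocol 8.3, 8.3.1 and 8.3.3 keep up the follow-up of serious, related and specially monitored events.
- Section 7.2 is worded as advice, with Medical Monitor contact where possible. Medicines given to treat an adverse event are exempt in Table 6-3, though that exemption is not on the vaccine row. Surgery counts only in the Sampling Period, and illness only if it interferes with participation.
- Section 10.9.2 is a specific provision for a named risk and need not contradict a general rule.

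A reader might go further and infer four things that the documents do not support.

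- *That TEAE incidence is necessarily biased low because ill participants are removed.* The triggering illness is itself recorded as a TEAE and she stays in the Safety Set, so she already counts as having an event. Only different, later events can be missed, and noncompliance and vaccination are not safety outcomes.
- *That any vaccine costs milk data.* A vaccine in week 3 or 4 falls after the 144 h collection. With earlier withdrawal, samples already taken stay in the PK Set, which needs only a full dose and one valid concentration.
- *That withdrawn participants are exchanged for event-free ones.* Replacement is optional, and the person replaced is not dropped from the Safety Set or PK Set.
- *That a woman planning a non-live vaccine is bound to be enrolled, dosed and withdrawn.* Inclusion criterion 11 requires consent to comply with the protocol's restrictions, which include the vaccine ban. The mismatch with exclusion 14 is real, but that sequence is not established.

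What the reply does not answer is why the assessment that closes the safety endpoint should be optional for a participant already dosed. The continuing duties in 8.3 do not schedule detection of new non-serious events, and SAP 4.3.1.2 plans counts and percentages without saying how shortened observation is handled.

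**Conclusion.** The point holds as a risk to completeness, not as a demonstrated bias. After the only dose, Protocol 7.2 ends data collection and leaves the Day 57 call to encouragement. If the call is missed after withdrawal at 144 h, 50 of 56 days (89%) of that participant's TEAE window have no scheduled contact. Withdrawal between 24 and 96 h leaves 10 to 4 of 15 milk intervals uncollected; withdrawal after 144 h leaves none. One participant is 6.7% to 8.3% of the planned number.

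The TEAE figure assumes that the call does not take place, and the milk figures disregard any EW sample. The withdrawal rates of 5% to 20% are assumptions. The change is worth making because the loss is avoidable and the study is small. The planned PK summaries would probably survive without it.

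**What to change.** In Protocol 7.2, add that once rozanolixizumab has been given:
- a prohibited medication or vaccine, or noncompliance, is recorded as a protocol deviation and does not by itself end data collection;
- after illness or surgery, the milk, blood and AE assessments already scheduled continue as far as the participant is willing and the investigator judges appropriate, with affected PK data flagged;
- the Day 57 call stays scheduled for every dosed participant unless she withdraws consent. Section 4.1.3 and the schedule footnote on early withdrawal should be aligned.

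Reconcile 7.2 with 10.9.2 on aseptic meningitis, and Table 6-3 (all vaccines) with exclusion criterion 14 (live vaccines only). Which vaccine rule applies is for the sponsor to decide, and how illness or surgery is managed remains with the investigator and sponsor.

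The cost is an amendment to wording. No visits are added, because the samples and the call are already in the schedule. The downside is that some PK profiles will carry a deviation flag.
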